5.4.3. Response Based on MADRS Total Score

5.4.3.1. Definition

A participant is defined as a responder at a given time point if the percent improvement from Study 54135419TRD3013 baseline in MADRS is \geq 50% at that time point (i.e., percent change \leq -50%) or if the MADRS total score is \leq 10. Participants who do not meet such criterion will be considered as non-responders.

5.4.3.2. Analysis

The number and percentage of participants who achieve a response will be summarized at each time point for observed case data.

5.4.4. Remission Based on MADRS Total Score

5.4.4.1. Definition

See Section 5.4.1.1.

5.4.4.2. Analysis

The number and percentage of participants who achieve remission will be summarized at each time point for observed case data.

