The dose of esketamine at the end-of-study visit (ie, esketamine becomes accessible locally) is not mandatory, this dose may be administered to allow time for transition to commercially available esketamine nasal spray. For subjects who receive a dose of esketamine nasal spray at the end-of-study visit, they will return for a safety follow-up visit 2 weeks after this visit.

For subjects who complete through end-of-study and do not administer a dose of esketamine nasal spray at this visit: 1) if participant's last dose was 2 weeks before this visit (ie, every 2 week dosing), then this visit is also considered the safety follow-up visit; or 2) if participant's last dose was 1 week before this visit (ie, once-weekly dosing), then the participant will return for the safety follow-up visit 1 week after this visit.

Refer to Section 6.6, for information regarding access to esketamine nasal spray following completion of the study.

Early Study Withdrawal Visit

If a participant withdraws from the study, an early study withdrawal visit should be conducted unless they withdraw consent, are lost to follow-up, or have died. If the early study withdrawal visit is conducted on the same day as a scheduled visit, duplicate assessments are not required.

If the early study withdrawal visit is performed 2 weeks or more after their last dose of esketamine nasal spray, this visit is also considered the safety follow-up visit.

Safety Follow-Up Visit

For participants who complete the study, the safety follow-up visit will be performed 2 weeks after the last nasal treatment session.

For participants who withdraw early from the study, all safety follow-up visit assessments as specified in the Schedule of Activities will be performed 2 weeks after their last dose of esketamine nasal spray unless they withdraw consent, are lost to follow-up, or have died.

If the safety follow-up visit is conducted on the same day as a scheduled visit (eg, early withdrawal visit performed 2 weeks after last dose of esketamine nasal spray), duplicate assessments are not required.

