7.2. Participant Discontinuation/Withdrawal From the Study

A participant will be withdrawn from the study for any of the following reasons:

- The participant discontinues study intervention (see Section 7.1)
- Esketamine nasal spray becomes accessible in an individual's local country
- Lost to follow-up
- Withdrawal of consent
- Death

When a participant withdraws before study completion, the reason for withdrawal is to be documented in the eCRF and in the source document. If the reason for withdrawal from the study is withdrawal of consent then no additional assessments are allowed.

Refer to Section 4.4 for study completion definition for participants.

Withdrawal of Consent

If a participant is unable to return for scheduled visits, it does not necessarily constitute withdrawal of consent. Alternate follow-up mechanisms that the participant agreed to when signing the consent form apply, as local regulations permit.

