1.2. Study Design

Study design and patient selection

This study is a single-arm, 2-year open-label extension to Study 54135419TRD3013 (ESCAPE-TRD study). The study 54135419TRD3013, was an open-label, randomized, active-controlled study to evaluate the efficacy, safety, and tolerability of flexibly dosed esketamine nasal spray compared with quetiapine extended release, both in combination with a continuing SSRI/SNRI, in participants 18 to 74 years of age, inclusive, with treatment-resistant Major Depressive Disorder. 676 participants were randomized in Study 54135419TRD3013 (ESCAPE-TRD) to receive either esketamine (N=336) or quetiapine (N=340) [CSR 54135419TRD3013 2023]. Participants who were randomly assigned to the esketamine arm in Study 54135419TRD3013 (ESCAPE-TRD study), up to N=336, , had esketamine nasal spray administered through Week 30 (every 2 week dosing) or Week 31 (once weekly dosing), completed the maintenance phase at Week 32, continue to benefit from esketamine nasal spray in combination with a continuing SSRI/SNRI in the opinion of the investigator, and commercial esketamine nasal spray is not accessible to them in their country, are eligible to enter this open-label extension study (Study 54135419TRD4010). At any point during the long-term extension study, participants who, in the opinion of the investigator, are no longer benefiting from treatment with esketamine nasal spray in combination with an SSRI/SNRI should be discontinued from the study; these participants will complete the early study withdrawal visit and then return for the safety follow-up visit 2 weeks (±2 days) after their last dose of esketamine nasal spray, unless they withdraw consent, are lost to follow-up, or have died.

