5.4.7.2. Analysis

The number and percentage of participants who achieve response will be summarized at each time point for observed case data.

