5.4.8.2. Analysis

The number and percentage of participants who achieve a remission of depressive symptoms will be summarized at each time point for observed case data.

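### MADRS and PHQ-9 response and remission are planned for observed cases only, so later-visit percentages are expected to exceed those among all treated participants

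*SAP*

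**What the plan says.** Four binary outcomes in the SAP's secondary endpoint section share one rule.

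- MADRS response (SAP 5.4.3.2): "The number and percentage of participants who achieve a response will be summarized at each time point for observed case data".
- MADRS remission (SAP 5.4.4.2): "The number and percentage of participants who achieve remission will be summarized at each time point for observed case data".
- PHQ-9 response (SAP 5.4.7.2): "The number and percentage of participants who achieve response will be summarized at each time point for observed case data".
- PHQ-9 remission (SAP 5.4.8.2): "The number and percentage of participants who achieve a remission of depressive symptoms will be summarized at each time point for observed case data".

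Protocol 4.1 and SAP 1.2 say that participants who, in the investigator's opinion, "are no longer benefiting from treatment with esketamine nasal spray in combination with an SSRI/SNRI should be discontinued from the study". Protocol 7.2 lists, among the reasons for withdrawal from the study, "The participant discontinues study intervention (see Section 7.1"). Protocol 4.1 adds: "If a participant withdraws from the study, an early study withdrawal visit should be conducted unless they withdraw consent", with loss to follow-up and death as the other exceptions. The Schedule of Activities includes MADRS and PHQ-9 at that visit.

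A separate exit is administrative. Once esketamine becomes accessible in a country, all participants there stop and are treated as completers (Protocol 4.1 and 4.4; SAP 5.2).

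**The concern.** In an observed-case percentage, a participant who has left is in neither the numerator nor the denominator. Here leaving is tied to outcome by the design: investigators are told to discontinue people who no longer benefit, and nobody is followed for efficacy after stopping treatment beyond the withdrawal visit. At later visits the tables describe mainly those still judged to benefit.

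At stake is how the Week 104 response and remission figures will be read. A reader is likely to take them as the share of the extension cohort doing well after two years, whereas they give the share among those who remained. No planned analysis of these four outcomes in the whole treated set counts the leavers.

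**Working it through.** **Inputs.** The documents give an expected enrolment of 100 to 200 (Protocol 9.2, SAP 3) and no expected remission rate, response rate or dropout rate. There is no planned figure to reproduce. Everything below uses assumed values: N = 150 treated, 90 in remission (60%), and withdrawal shares of 10%, 20% and 30%.

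**Formulas.** Let R be the number in remission who remain, D the number withdrawn, and d = D/N.

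- Observed-case percentage = R/(N − D).
- Percentage with leavers counted as non-remitters = R/N.
- Ratio of the two = 1/(1 − d).

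**Case 1: nobody's status changes and all leavers are non-remitters.**

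| Withdrawn | Observed case | All treated | Ratio |
|---|---|---|---|
| 10% (15) | 90/135 = 66.7% | 90/150 = 60.0% | 1.11 |
| 20% (30) | 90/120 = 75.0% | 90/150 = 60.0% | 1.25 |
| 30% (45) | 90/105 = 85.7% | 90/150 = 60.0% | 1.43 |

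The exact 95% interval for 90/150 is 51.7% to 67.9%. The percentages do not depend on N, so they are the same at 100 and at 200.

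**Case 2: some leavers are in remission** (30 of 150 leave; 90 of the 150 are in remission).

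| Share of leavers in remission | Observed case | Leavers counted as non-remitters | Full cohort |
|---|---|---|---|
| 0% | 90/120 = 75.0% | 90/150 = 60.0% | 60.0% |
| 30% | 81/120 = 67.5% | 81/150 = 54.0% | 60.0% |
| 60% | 72/120 = 60.0% | 72/150 = 48.0% | 60.0% |
| 80% | 66/120 = 55.0% | 66/150 = 44.0% | 60.0% |

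The upward bias disappears if leavers are in remission as often as the cohort, and reverses if they are in remission more often. The removal rule makes both unlikely. The third column shows that counting leavers as failures errs the other way whenever some of them were well.

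**Case 3: change over time.** Suppose 105/150 (70%) start in remission, and 30 of them relapse and are withdrawn. Observed-case remission is 75/120 = 62.5%; among all treated it is 75/150 = 50.0%. The observed-case figure falls over time and still overstates.

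**Case 4: country-access exits.** Suppose 20% (30) leave for commercial access regardless of status, so 120 remain, 72 of them in remission, and 24 of the 120 are withdrawn as non-remitters.

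- Observed case: 72/96 = 75%.
- Access exits removed from the denominator, other leavers counted as non-remitters: 72/120 = 60%.
- All exits counted as non-remitters: 72/150 = 48%.

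Access exits unrelated to status do not bias the observed-case figure; treating them as failures would introduce a bias.

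**The case against.** The strongest reply is that these tables are not where the study judges efficacy. Protocol 3 states the long-term efficacy objective as the proportion relapse-free at Week 104. SAP 5.4.1.1 defines that endpoint as no relapse and no discontinuation of any component of study intervention, so leavers count as failures. Response and remission are SAP additions, the study has no hypothesis, and Protocol 9.4.1 announces by-visit descriptive statistics of observed values. This stands in part: no error rate is affected, and the stated objective is partly protected. But the relapse-free proportion is confined to participants in remission at Week 8 of TRD3013. It does not cover response, PHQ-9 or the full Safety/Efficacy set.

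Other points on that side:

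- The withdrawal visit can bring a leaver's last poor score into a table. True, but under SAP 5.1.1 it can supply only one visit window, so the selection is delayed rather than removed. That section allows a visit to be reused for an endpoint time point, yet 5.4.3 to 5.4.8 define no such summary. The visit-window file it cites is not available for checking.
- Removal rests on investigator opinion, not on a MADRS cut-off, so some non-remitters will stay. This limits the size of the bias but does not change its expected direction.
- Counts accompany the percentages, and disposition is tabulated with reasons (SAP 5.2). The two are not linked by visit, so an all-treated percentage can only be approximated.

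Three stronger readings are tempting and not supported. A reader might infer that the percentages must rise over time; Case 3 shows otherwise. A reader might infer that the study cannot answer its long-term efficacy question; the relapse endpoint addresses it in part. A reader might also blame the removal of the MMRM in SAP version 2. Such a model analyses continuous scores and does not itself give response or remission percentages, and the version history does not say which outcomes it covered. Nor do the definitions labelling those who miss the criterion as non-responders (5.4.3.1, 5.4.7.1) rescue the tables: they classify observed scores and give no rule for missing visits.

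**Conclusion.** The point holds for the four response and remission tables. Their later-visit percentages are expected to exceed the percentage among all treated participants, because the design removes people who do poorly and the tables then ignore them.

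The direction rests on leavers being in remission or response less often than those who stay, which the removal rule makes likely but does not guarantee. The size cannot be derived from the documents; the overstatement of 6.7, 15.0 or 25.7 percentage points in Case 1 is illustrative and assumes that every leaver is a non-remitter. This is a gap in descriptive reporting that is cheap to close, not a failure of the primary safety analysis or of the relapse-free endpoint.

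**What to change.** Keep the observed-case tables and show the number observed out of the number treated at each visit. Add one supplementary table of MADRS and PHQ-9 response and remission on the Safety/Efficacy set, with these rules:

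- Participants who left for lack of benefit, relapse, adverse event, consent withdrawal, loss to follow-up or death count as non-responders and non-remitters from then on.
- Participants who left because esketamine became commercially accessible leave the denominator from then on. SAP 5.2 counts them as completers, so they must be separated from those who reached Week 104.
- The remaining exit reasons in Protocol 7.1 are assigned in advance to one of these two groups.
- A stated rule covers intermittent missed visits.

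Report the observed-case and supplementary figures side by side at Week 104, neither replacing the other.

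The cost is one extra table, built mainly from disposition data that the SAP already summarises. Its percentage will be less favourable and should be labelled a conservative lower estimate, because some leavers may have been in remission: in Case 2 with 30% of leavers in remission it gives 54.0% against 60.0% for the full cohort.

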5.4.5. Clinical Global Impression – Severity (CGI-S)

5.4.5.1. Definition

The CGI-S provides an overall clinician-determined summary measure of the severity of the participant's illness that takes into account all available information, including knowledge of the participant's history, psychosocial circumstances, symptoms, behavior, and the impact of the symptoms on the participant's ability to function. (Guy 1991) The CGI-S evaluates the severity of psychopathology on a scale of 1 to 7. Considering total clinical experience with the depression population, a participant is assessed on severity of illness at the time of rating according to: [0=not assessed; 1=normal (not at all ill); 2=borderline ill; 3=mildly ill; 4=moderately ill; 5=markedly ill; 6=severely ill; 7=among the most extremely ill patients].

A score of 0 indicates that the participant was not assessed, and will be treated as missing. The score from 1 to 7 will be summarized as recorded.

Negative changes in CGI-S score indicate improvement.

5.4.5.2. Analysis

Descriptive statistics of the actual values and the change from Study 54135419TRD3013 baseline will be presented for observed case data.

Mean score (+/- SE) and mean changes from baseline (+/- SE) will be presented graphically over time.

A frequency distribution over time of the CGI-S scores at each scheduled visit will be provided for observed case data.

5.4.6. Patient Health Questionnaire - 9 Item (PHQ-9)

5.4.6.1. Definition

The 9-item Patient Health Questionnaire - 9 Item (PHQ-9) scale scores each of the 9 symptom domains of the DSM-5 MDD criteria and it has been used both as a screening tool and a measure of response to intervention for depression. Each item is rated on a 4-point scale (0=not at all, 1=several days, 2=more than half the days, and 3=nearly every day). The participant's item responses are summed to provide a total score (range of 0 to 27), with higher scores indicating greater severity of depressive symptoms. The recall period is 2 weeks.

Negative changes in PHQ-9 total score indicate improvement.

5.4.6.2. Analysis

Descriptive statistics of the actual values and the change from Study 54135419TRD3013 baseline to each postbaseline time point will be presented for PHQ-9 total score for observed case data. Mean total score (+/- SE) and mean changes from baseline (+/- SE) will be presented graphically over time.

Frequency distributions of the responses to the question "How difficult have these problems made it for you to do your work, take care of things at home, or get along with other people" will be provided at each assessment time point for observed case data.

5.4.7. Response Based on PHQ-9 Total Score

5.4.7.1. Definition

A participant is defined as a responder at a given time point if the percent improvement from Study 54135419TRD3013 baseline in PHQ-9 total score is ≥50% at that time point. Participants who do not meet such criterion will be considered as non-responders.

Negative percent changes in PHQ-9 total score indicate improvement (eg, percent change < -50% indicates improvement >50%).

5.4.7.2. Analysis

The number and percentage of participants who achieve response will be summarized at each time point for observed case data.

5.4.8. Remission Based on PHQ-9 Total Score

5.4.8.1. Definition

A participant is defined as a remitter at a given time point if the PHQ-9 total score is ≤ 9 at that time point. Participants who do not meet such criterion will be considered as non-remitters. As a sensivity analysis, remission will be defined as a PHQ-9 total score ≤ 4 .

5.4.8.2. Analysis

The number and percentage of participants who achieve a remission of depressive symptoms will be summarized at each time point for observed case data.

5.4.9. European Quality of Life (EuroQol) Group, 5 Dimension, 5-Level questionnaire (EQ-5D-5L)

5.4.9.1. Definition

The EQ-5D-5L is a standardized instrument for use as a measure of health outcome, primarily designed for self-completion by respondents. It is a descriptive system comprised of the following 5 dimensions: Mobility, self-care, usual activities, pain/discomfort and anxiety/depression. Each of the 5 dimensions is divided into 5 levels of perceived problems (Level 1 indicating no problem, Level 2 indicating slight problems, Level 3 indicating moderate problems, Level 4 indicating

severe problems, and Level 5 indicating extreme problems). (EuroQol Group 2014, EuroQol Group 2013)

Participants select an answer for each of the 5 dimensions considering the response that best matches their health "today". Individual scores from the 5 dimensions will be used to obtain a weighted health status index as shown below: (i) Scores from each dimension will be combined to obtain a 5L profile score: eg, a score of 1 for each dimension will give a 5L profile score of 11111. Dimension scores will be combined in the following order: Mobility, Self-Care, Usual Activities, Pain/Discomfort, Anxiety/Depression. (ii) The EuroQol Group coordinated a study that administered both the 3-level and 5-level versions of the EQ-5D, in order to develop a "crosswalk" between the EQ-5D-3L value sets and the new EQ-5D-5L descriptive system, resulting in crosswalk value sets for the EQ-5D-5L. *Interim Scoring for the EQ-5D-5L: Mapping the EQ-5D-5L to EQ-5D-3L Value Sets (Van Hout et al, 2012)*; (iii) The UK value set will be used to get the health utility values for all the countries participating in the study. See "EQ-5D-5L Crosswalk Value Sets.xls".

A sum score, with a possible range of 0 to 100, is derived as follows: (sum of the scores from the 5 dimensions minus 5) * 5. Negative changes in the sum score indicate improvement.

5.4.9.2. Analysis

Descriptive statistics of the actual values and the change from Study 54135419TRD3013 baseline to each postbaseline time point will be presented for weighted EQ-5D health status index, the EQ-VAS, and the sum score for observed case data. Mean values and mean changes from baseline (+/-SE) will be presented graphically over time.

Individual dimension responses will also be summarized at each visit with frequency counts and percentage of participants for observed case data.

5.5. Exploratory Endpoint(s) Analysis

In cases where the oral AD is switched to another compound from the SNRI/SSRI classes during Study 54135419TRD4010, the impact of switching will be explored. The reasons for the switches will be summarized, the impact on existing AEs will be described (outcome of AEs ongoing at the time of switching will be tabulated), and new AEs starting after the switches will be tabulated. Also, the impact on the efficacy parameters MADRS and CGI-S will be explored by summarizing the observed values at the visit when the switch was made and changes from that visit at subsequent visits. Furthermore, a listing will be created for the participants who switch to another compound from the SNRI/SSRI classes during Study 54135419TRD4010.

5.6. Other Safety Analyses

All safety analyses will be based on the Safety analysis set using data from Study 54135419TRD3013 and Study 54135419TRD4010, unless otherwise specified.

For all continuous safety variables, descriptive statistics will include the N, mean, standard deviation (SD), median, minimum, and maximum. Categorical variables will be summarized using frequency counts and percentages.

5.6.1. Extent of Exposure

Total exposure during both Study 54135419TRD3013 and Study 54135419TRD4010 is described, unless specified otherwise.

The number and percentage of participants who receive each study agent within the study intervention will be summarized.

Descriptive statistics for duration of study intervention (N, mean, SD, median, and range (minimum, maximum)) will be summarized. Study intervention duration is defined as (date of last dose of study intervention) +1.

A frequency distribution of the total number of dosing sessions of intranasal study medication will be presented.

Modal dose for a subject is defined as the most frequently taken dose by a subject. Mean dose of a subject is calculated as the sum of doses divided by the total number of days. The final dose is the last non-zero dose received. The calculation of mean, modal and final dose will exclude days off study drug.

Descriptive statistics (N, mean, SD, median, minimum and maximum) of modal dose, mean and final dose will be presented for oral AD. For esketamine a frequency distribution will be presented for modal dose and final dose and descriptive statistics (N, mean, SD, median, minimum and maximum) will be presented for mean dose.

For esketamine NS, the number (%) of participants with a dose adjustment/dose frequency adjustment/dose not administered during Study 54135419TRD4010 will be summarized. Reasons for doses not administered will also be summarized. For oral AD, the number (%) of participants with a dose adjustment during Study 54135419TRD4010 will be summarized. Reasons for dose adjustments will also be summarized.

The number (%) of participants with a swith of oral AD during Study 54135419TRD4010 will be summarized.

